### **9.2 Efficacy Analysis**

#### **9.2.1 Analysis Populations**

The following subject populations will be assessed:

##### *Full-Analysis-Set (FAS) Population*

The FAS will include all participants who are enrolled. The FAS will be the primary population for evaluating all efficacy endpoints and participant characteristics.

##### *Safety-Analysis-Set (SAT) Population*

The SAT Population will include all subjects who receive at least 1 dose of study medication. The SAT Population will be the primary population for evaluating

treatment administration/compliance and safety. Efficacy endpoints may be assessed in this population as well.

### **9.2.2 Definition of Primary Endpoint**

Pathological complete remission (pCR): It is defined as absence of any residual cancer cell in both the primary tumor lesion and lymph node specimens assessed post-surgery.

### **9.2.3 Analysis of Primary Endpoint**

Pathological complete response (pCR): It refers to absence of any residual cancer cell in both the primary tumor lesion and lymph node specimens assessed post-surgery.

Descriptive data analyses will be conducted for both primary and secondary objectives. Categorical variables will be summarized including the number of non-missing observations, the frequency of the observed endpoint as well as the observed proportion. Continuous variables will be summarized including the number of non-missing observations, mean (Standard Deviation [SD]), median, Q1, Q3, and the minimum/maximum.

- pCR will be summarized using frequency counts and percentages with 95% CIs.
- Continuous variables in surgical outcomes will be summarized using median and range.

Categorical variables in surgical outcomes, safety and tolerability will be summarized using frequency counts and percentages.

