Lorlatinib will be administered orally QD at approximately the same time of the day on a continuous daily dosing schedule, ie, without a break in dosing in the absence of drug-related toxicity. Patients must swallow the study medication whole and must not manipulate or chew the medication prior to swallowing. Patients should be instructed to take their medication at approximately the same time every day. A dosing card will be provided to the patients to provide guidance for the correct use of lorlatinib. Patients must be instructed that should they miss a dose or vomit any time after taking a dose, they must not “make it up” with an extra dose. Instead, resume the subsequent doses as originally prescribed. Any missed dose may be taken up to 6 hours prior to the next scheduled dose, otherwise it should be skipped and dosing resumed with subsequent doses as prescribed. The patient must be instructed to record all doses (including missed or vomited) in a dosing diary supplied by the site. If doses are missed or vomited, this must be indicated in the source documents and Case Record Forms (CRFs).

The response to neoadjuvant therapy will be evaluated by the investigators utilizing RECIST 1.1 criteria. Patients demonstrating no progressive disease as per these criteria will proceed to surgical resection with radical intent, scheduled within 6 weeks following the conclusion of lorlatinib neoadjuvant therapy. Patients completing the surgical intervention and pathological evaluation will conclude their participation in this study within 1-month post-surgery and may continue to receive subsequent treatment as deemed appropriate by their healthcare providers, based on prevailing clinical practice.

This study will intermittently collect blood specimens from patients at baseline, during neoadjuvant therapy, and perioperatively to explore changes in tumor biomarkers. Baseline and postoperative tissue specimens will be obtained, and Whole Exome Sequencing (WES) will be performed to investigate the correlation between neoadjuvant therapy efficacy and tissue mutation changes. Additionally, tissue

mutation results will be used to customize a blood testing panel to enhance detection rates.

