### **9.1 Sample Size Determination**

According to the Simon's 2-stage mini-max design, the null hypothesis that the PCR rate is  $\leq 10\%$  will be tested against a 1-sided alternative. In the first stage, 15 patients will be accrued. If there are 1 or fewer pCR in these 15 patients, the study will be stopped early for futility. Otherwise, 10 additional patients will be accrued for a total of 25. The null hypothesis will be rejected if 6 or more PCR are observed in 25 patients. This design yields a type I error rate of 0.05 and power of 0.80 when the true PCR rate is 30%.

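### The plan does not say how patients without a surgical specimen count towards pCR and MPR, and its summary rule can be read as a resected-only rate

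*Protocol*

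**What the plan says.** - **Endpoint (Protocol 9.2.2).** pCR is "absence of any residual cancer cell in both the primary tumor lesion and lymph node specimens assessed post-surgery". MPR in 9.2.4 likewise rests on viable tumour in the resected primary and resected nodes. Neither definition gives a value to a patient with no specimen.
- **Route to surgery (Protocol 3.1; Synopsis, Methods).** "Patients demonstrating no progressive disease as per these criteria will proceed to surgical resection with radical intent". Section 6.4.8 lists progression, unacceptable toxicity, deterioration and the patient's own choice among reasons for withdrawal. The Synopsis adds that no data are collected after withdrawal.
- **Summary rule (Protocol 9.2.3, repeated in 9.2.5 and the Synopsis).** "Categorical variables will be summarized including the number of non-missing observations, the frequency of the observed endpoint as well as the observed proportion". A further line asks for counts and percentages with 95% CIs and does not name the divisor.
- **Population (Protocol 9.2.1).** The FAS is all enrolled participants, and "The FAS will be the primary population for evaluating all efficacy endpoints and participant characteristics". The Synopsis instead defines the efficacy set as all patients with at least one dose.
- **Decision rule (Protocol 9.1).** The unit is the accrued patient: "In the first stage, 15 patients will be accrued". Futility is declared at 1 or fewer pCR in that group. If the trial goes on, accrual rises by 10 to 25 in all, and 6 or more pCR reject the null.

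**The concern.** A patient who is not resected has no pathology result. A programmer who follows the summary rule could tabulate that patient as missing and divide by those with a result. The result may be absent because treatment failed, progression being the clearest case, so such values are not missing at random. Leaving them out can only raise the rate.

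The reported pCR rate would then be conditional on reaching surgery, yet it would be read against a 10% null and a 30% alternative that 9.1 sets for accrued patients. The MPR rate has the same problem. The trial is open-label and pathology is assessed locally by the investigator, so the denominator should be fixed before any result is known.

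**Working it through.** **Inputs.** From Protocol 9.1: stage 1 n = 15, stop at 1 or fewer pCR; total n = 25, reject at 6 or more; null 10%, alternative 30%; stated type I error 0.05 and power 0.80. The protocol gives no non-resection rate. I assume m = 0 to 5 of 25 unresected (0 to 20%).

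**Step 1: reproduce the design.** The probability of rejection at true rate p is

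P(reject) = sum over x = 2 to 15 of Bin(x; 15, p) × P(Bin(10, p) ≥ 6 − x), where the second factor is 1 once x ≥ 6.

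- p = 0.10: 0.0328, within the stated 0.05.
- p = 0.30: 0.8017, matching the stated 0.80.

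A search over two-stage designs with type I error at most 0.05 and power at least 0.80 returns the same minimax design (15, stop at 1 or fewer; 25, reject at 6 or more). The design is sound as stated, with accrued patients as its unit.

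**Step 2: the reported rate under each denominator.** An unresected patient cannot be a pCR, so the numerator is the same on both readings. Dividing by patients with a specimen multiplies the rate by 25/(25 − m). The protocol names no interval method for pCR, so I use the exact (Clopper-Pearson) interval: lower limit = 0.025 quantile of Beta(x, n − x + 1), upper limit = 0.975 quantile of Beta(x + 1, n − x). Take x = 6, the smallest count that rejects the null.

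| Unresected (assumed) | pCR / divisor | Rate | 95% CI |
|---|---|---|---|
| 0, or all counted as non-pCR | 6/25 | 24.0% | 9.4 to 45.1 |
| 1 | 6/24 | 25.0% | 9.8 to 46.7 |
| 2 | 6/23 | 26.1% | 10.2 to 48.4 |
| 3 | 6/22 | 27.3% | 10.7 to 50.2 |
| 5 | 6/20 | 30.0% | 11.9 to 54.3 |

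With 2 or more unresected, the lower limit moves from below to above the 10% null rate. With 5, the minimum success count displays the 30% design alternative although the all-enrolled rate is 24%. The factor 25/(25 − m) applies equally to MPR.

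**Step 3: the decision rule.** Section 9.1 counts pCR among accrued patients. An unresected patient adds nothing to the count and stays among the 15 or the 25. The rejection probabilities in step 1 therefore stand whichever divisor is used for the reported percentage.

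**The case against.** The strongest reply is that nothing in the protocol actually drops anyone. Section 9.2.3 lists three things to report and does not make the first the divisor of the third; it is generic wording for all categorical variables. The FAS, the synopsis efficacy set and the Simon rule all point to an all-patient denominator, no resected-only set is defined, and a patient without a tumour-free specimen arguably just fails the pCR definition. Handling of non-evaluable patients is often left to the SAP, which is not shown.

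Much of this stands. A reader might infer that treatment failures certainly fall out of the primary rate; the text supports only that they can. Four other inferences also go too far:

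- *Progressing patients are barred from surgery.* Section 3.1 makes absence of progression the condition for proceeding and states no explicit ban.
- *Stopping for toxicity means no pCR value.* Section 5.2 keeps such patients in the trial, and the stated condition for surgery is no progression, so they may still be resected.
- *Type I error is inflated.* If the 25 meant patients with specimens, a 10% per-enrolled rate would become 0.10/(1 − f) among resected patients. Rejection would then have probability 0.039, 0.047, 0.056 and 0.082 at f = 4%, 8%, 12% and 20% unresected. Section 9.1 says accrued, so this does not apply.
- *The alectinib background trial shows non-resection.* Its 8 R0 resections among 9 patients describe margin status and do not show that the ninth was unresected.

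What the reply does not remove is the ambiguity. A population says who enters the analysis, not how a member without a value is counted. The protocol shows this itself: 9.2.5 puts all analyses on the FAS, while 9.2.4 takes nodal downstaging only among patients who completed treatment. Nor is this mere silence left to the SAP. The protocol already states a summary rule for the primary endpoint, and section 9 requires major changes to that endpoint or its analysis to appear in a protocol amendment.

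**Conclusion.** The point holds as an ambiguity that should be closed. Two denominators are available for the primary estimate, and the one suggested by the non-missing wording is inconsistent with the FAS and with the accrual-based design. If it were used, the reported pCR rate at the minimum success count would rise from 24.0% to 26.1% with 2 unresected and to 30.0% with 5. The first of these already lifts the lower confidence limit above 10%.

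These sizes rest on assumed numbers unresected, on exact single-sample intervals, and on a count of 6. With 2 or 3 unresected the shift is 2 to 3 percentage points, small against an interval of about 9% to 45%. The go/no-go decision is untouched (type I error 0.0328, power 0.8017). The exposure lies in the reported pCR and MPR rates and their intervals. An unseen SAP may already settle it.

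**What to change.** - In 9.2.2 to 9.2.5, state that any FAS patient without an evaluable surgical specimen, for any reason, counts as non-pCR and non-MPR.
- Name the FAS as the denominator for both rates and their 95% CIs.
- Keep the number of patients with an evaluable specimen as a reported count, and say that it is not the divisor. Label any resected-only rate as supplementary.
- Reconcile the synopsis efficacy set (at least one dose) with the FAS in 9.2.1 (all enrolled), so that an enrolled but undosed patient is treated the same way throughout.

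The cost is a wording change to the protocol, carried into the SAP. Sample size, stopping rule and data collection stay as they are. The downside for the sponsor is a slightly less favourable headline rate if any patient is not resected.

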#### **9.2.5 Analysis of Secondary Endpoints**

All analyses will be performed using the FAS.

Objective Response on each treatment arm will be summarized based on the investigator's assessment. The number and percent of subjects achieving objective response (CR or PR) will be summarized along with corresponding 2-sided 95% CI using the binomial distribution.

MPR rate refers to the proportion of patients  $\leq 10\%$  residual viable tumor cells histologically detected in the resected primary tumor and all resected lymph nodes after surgery assessed by the investigator.

Descriptive data analyses will be conducted for both primary and secondary objectives. Categorical variables will be summarized including the number of non-missing observations, the frequency of the observed endpoint as well as the observed proportion. Continuous variables will be summarized including the number of non-missing observations, mean (Standard Deviation [SD]), median, Q1, Q3, and the minimum/maximum.

- MPR, and ORR will be summarized using frequency counts and percentages with 95% CIs.
- Continuous variables in surgical outcomes will be summarized using median and range.

Categorical variables in surgical outcomes, safety and tolerability will be summarized using frequency counts and percentages.

Descriptive statistics will be used to summarize subject characteristics, study conduct, subject disposition, treatment administration/compliance, and safety parameters.

Data will also be displayed graphically, where appropriate.

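### Does a descriptive 95% CI for pCR conflict with the one-sided 5% Simon rule at the success boundary of 6/25?

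*Protocol*

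**What the plan says.** Section 9.1 (repeated in the synopsis under Sample Size Determination) sets up a Simon minimax design for pCR. The null rate is 10% or less and "will be tested against a 1-sided alternative". Fifteen patients enter stage 1, and the trial stops for futility at 1 or fewer pCRs. Otherwise 10 more are enrolled, and "The null hypothesis will be rejected if 6 or more PCR are observed in 25 patients". The stated operating characteristics are type I error 0.05, and power 0.80 at a true rate of 30%.

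Section 9.2.3 covers the analysis of the primary endpoint. It says that "Descriptive data analyses will be conducted for both primary and secondary objectives" and that "pCR will be summarized using frequency counts and percentages with 95% CIs". It does not restate the null rate, the boundary or the two stages, and it names neither the interval method nor its sidedness.

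The only interval method in the protocol is in Section 9.2.5, where objective response is to be given with the "corresponding 2-sided 95% CI using the binomial distribution". That sentence is about ORR, not pCR. Section 9 leaves detailed methodology to a separate SAP.

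**The concern.** The sample-size section describes a hypothesis test, and the primary-analysis section describes a summary. Nothing in the text links the two. The levels also differ: the test is one-sided at 5%, while a two-sided 95% interval has 2.5% in each tail. Where the one-sided p-value falls between 0.025 and 0.05, the test rejects 10% while an interval inverted from the same exact test still covers it.

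The success boundary is such a result. A report could then declare success on 6 of 25 beside an interval starting just below 10%. A reader who took exclusion of 10% as the criterion would in effect be demanding 7 of 25, for which the stated power of 0.80 no longer holds.

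**Working it through.** **Inputs (Section 9.1).** Null rate p0 = 0.10; alternative p1 = 0.30; n1 = 15, stop at 1 or fewer; n2 = 10; reject at 6 or more of 25. From Section 9.2.3: 95% level, method not stated.

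**Step 1: reproduce the design.** With X1 ~ Bin(15, p) and X2 ~ Bin(10, p),

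P(reject | p) = Σ over x1 = 2 to 15 of P(X1 = x1) × P(X2 ≥ 6 − x1).

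At p = 0.10:

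| x1 | P(X1 = x1) | P(X2 ≥ 6 − x1) | product |
|---|---|---|---|
| 2 | 0.2669 | 0.0128 | 0.0034 |
| 3 | 0.1285 | 0.0702 | 0.0090 |
| 4 | 0.0428 | 0.2639 | 0.0113 |
| 5 | 0.0105 | 0.6513 | 0.0068 |
| 6 or more | 0.0022 | 1 | 0.0022 |

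The sum is 0.0328 (from unrounded terms). At p = 0.30 the same formula gives 0.8017. A search over designs with type I error at most 0.05 and power at least 0.80 returns this one as minimax. Section 9.1 is therefore correct, with 0.05 a nominal ceiling and 0.033 the attained value.

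**Step 2: p-value at the boundary.** For a result of 6/25 the one-sided p-value equals the attained type I error: 0.0328 with the two-stage calculation, 0.0334 if the stages are ignored. Both lie between 0.025 and 0.05.

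**Step 3: 95% limits at 6/25 (24%).** The Clopper-Pearson lower limit is the 0.025 quantile of Beta(6, 20) = 9.36%, and the upper limit is the 0.975 quantile of Beta(7, 19) = 45.13%. The two-stage lower limit solves P(reject | p) = 0.025, giving 9.40%. The Wilson lower limit, with z = 1.96, is

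[0.24 + 3.84/50 − 1.96 × √(0.24 × 0.76/25 + 3.84/2500)] / (1 + 3.84/25) = (0.3168 − 0.1842)/1.1537 = 11.5%.

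| 95% method | lower limit at 6/25 | contains 10%? |
|---|---|---|
| Clopper-Pearson | 9.4% | yes |
| Two-stage exact | 9.4% | yes |
| Wald | 7.3% | yes |
| Mid-p | 10.3% | no |
| Jeffreys | 10.7% | no |
| Agresti-Coull | 11.2% | no |
| Wilson | 11.5% | no |

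**Step 4: neighbouring results.** At 7/25 every method excludes 10% (Clopper-Pearson 12.1% to 49.4%). At 5/25, which is not a rejection, all the 95% lower limits are below 10%. The mismatch is confined to exactly 6/25.

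**Step 5: how often.** P(total = 6 after passing stage 1) = P(reject at ≥ 6) − P(reject at ≥ 7).

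| true rate | P(exactly 6) | P(reject) | share of successes |
|---|---|---|---|
| 10% | 0.023 | 0.033 | 71% |
| 25% | 0.179 | 0.616 | 29% |
| 30% | 0.144 | 0.802 | 18% |
| 40% | 0.043 | 0.969 | 4.5% |

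If someone did require 7/25, power at 30% would be 0.8017 − 0.1439 = 0.658.

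**Step 6: would a 90% interval help?** At 6/25 the Clopper-Pearson 90% lower limit is 11.0% and the two-stage one-sided 95% bound is 11.1%, both above 10%. At 5/25 the Clopper-Pearson 90% lower limit is 8.2%. The exact 90% interval therefore agrees with the rule on both sides of the boundary. The Wilson 90% interval does not: at 5/25 its lower limit is 10.09%, which excludes 10% without a rejection. Agreement depends on method as well as level.

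**The case for a change.** The strongest case for a change is that this is more than missing detail. The protocol itself states a descriptive analysis at a 95% level for an endpoint that it tests one-sided at 5%. Section 9 says that a major modification of the primary analysis must also appear in a protocol amendment, so the protocol is arguably the place to settle the matter. The ORR wording in Section 9.2.5 makes an exact two-sided interval a natural guess for pCR too. The boundary is also the result where readers look hardest, and at a true rate of 25% it makes up 29% of successes.

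Some of this stands. Section 9.2.3 does not point back to 9.1, and an exact 95% interval at 6/25 would contain 10%. What does not stand is that the reader is left unsure which section governs. Section 9.1 gives a complete rejection rule, and 9.2.3 gives a format for summarising pCR with no competing criterion. Reporting a conventional two-sided 95% interval beside a one-sided phase II test is a choice of reporting level; the interval answers a question about precision. The interval method is ordinary SAP content.

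**Conclusion.** No change to the plan is needed. Followed as written, it gives a sound decision (reject at 6 or more of 25, attained type I error 0.033, power 0.802 at 30%) and a 95% interval for pCR. The apparent contradiction rests on assuming that the pCR interval is two-sided and exact (or Wald). Even then it arises at one outcome, 6/25, with probability 0.144 at the design alternative, and it does not alter the conclusion that Section 9.1 prescribes.

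Writing the rule into 9.2.3 would repeat 9.1, and adding a 90% interval would be a reporting preference; neither moves a boundary or an error rate. If the trial ends at 6/25, the analyst can cite the 9.1 rule as the basis for the conclusion, label the 95% interval as descriptive and, if a matching bound is wanted, give the two-stage one-sided 95% lower limit of 11.1%.

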#### **9.2.4 Definitions of Secondary Efficacy Endpoints**

Major pathologic response (MPR): defined as  $\leq 10\%$  residual viable tumor cells histologically detected in the resected primary tumor and all resected lymph nodes after surgery.

Objective response rate (ORR): defined as a complete response or a partial response at the presurgical radiologic evaluation, based on the investigator's assessment according to RECIST v1.1;

Surgical outcomes and intraoperative events:

Rate of lymph node downstaging: It is defined as the proportion of patients who have completed the neoadjuvant lorlatinib treatment before surgery and have achieved a N stage downing of the tumor as confirmed by CT evaluation after 6 weeks in all patients who have completed the treatment.

Unanticipated delays to surgery: It is defined as the proportion of patients who have unanticipated delays to surgery  $> 6$  weeks after completion of neoadjuvant treatment.

Surgical complication rate: It is defined as the proportion of patients who have completed the surgery after neoadjuvant lorlatinib treatment.

Safety and tolerability per NCI-CTCAE v5.0.

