## **3. STUDY DESIGN**

### **Figure 1. Study Design**

### 3.1 Study design

This protocol delineates a Phase II, open-label, single-arm, prospective, multi-center study designed to evaluate the efficacy and safety of lorlatinib as a neoadjuvant therapy in patients with resectable ALK-positive non-small cell lung cancer (NSCLC). [Figure 1]

Eligible participants include male and female subjects aged  $\geq 18$  years, diagnosed with clinical stage IB, II, IIIA, or selected IIIB (including T4N2, as per the American Joint Committee on Cancer [AJCC] 8th edition) NSCLC, as assessed by positron emission tomography/computed tomography (PET/CT), or through computed tomography (CT), abdominal ultrasound, cranial MRI/CT, and bone scintigraphy. Enrollment criteria mandate that all tumors must test positive for ALK rearrangement, verified through Ventana ALK (D5F3), next-generation sequencing (NGS), etc. testing methods. All tumors will be of histo- and/or cytopathology consistent with NSCLC. Performance status (ECOG) 0-1 at enrolment, with no deterioration over the previous 2 weeks prior to baseline or day of first dosing of lorlatinib.

Upon meeting eligibility criteria, patients will be registered to receive oral lorlatinib at a dose of 100mg once daily (qd) for a period of 6-8 weeks, assessment will be conducted after 4 weeks, as determined by the attending clinicians based on the best clinical

practice. The duration of neoadjuvant therapy has been designed to optimize treatment efficacy while ensuring the feasibility of subsequent surgical resection.

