### **7.2.2 Tumor Tissue**

Informed consent will be obtained prior to tissue acquisition and testing for each patient. After the last cycle of induction therapy, the tumor tissues will be collected immediately by surgical resection. Tumor and lymph node collection from definitive surgical resection and sampling of fresh tumor sample (as applicable dependent on the size of residual tumor) is mandatory on the day of surgery. Processing of the remainder of the specimens for histopathologic analysis should be performed within 72 hours of the procedure. Sections will be used for local pathology review assessing pCR and MPR.

Tumor tissue samples collected during the screening period and post-operation will be used for Whole Exome Sequencing (WES) to investigate the correlation between changes in tissue clonality and neoadjuvant therapy efficacy. Additionally, based on

tissue mutation results, a customized blood testing gene panel (PANEL) will be designed to enhance detection rates in blood samples. Residual specimens should be processed for histopathological analysis within 72 hours of collection. Sections will be reviewed by the local laboratory for pathological assessment to evaluate pCR and MPR.

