#### 46. Normal sites

47. Cystic lesions: Simple cysts should not be considered as malignant lesions and should not be recorded either as target or non-target disease. Cystic lesions thought to represent cystic metastases can be measurable lesions, if they meet the specific definition above. If non-cystic lesions are also present, these are preferred as target lesions.
48. Normal nodes: Nodes with short axis <10 mm are considered normal and should not be recorded or followed either as measurable or non-measurable disease.

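### Section 9.2.4 judges nodal downstaging on CT alone although the resected nodes are collected and read, so patients can be misclassified in either direction

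*Protocol*

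**What the plan says.** Section 9.2.4 defines the rate of lymph node downstaging as the share of patients who completed neoadjuvant lorlatinib and "have achieved a N stage downing of the tumor as confirmed by CT evaluation after 6 weeks". The denominator is stated as "in all patients who have completed the treatment". No pathological nodal stage is asked for.

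The protocol obtains that pathology anyway. Section 7.2.2 makes "Tumor and lymph node collection from definitive surgical resection" mandatory on the day of surgery and sends sections to local pathology review for pCR and MPR. Section 9.2.2 defines pCR as "absence of any residual cancer cell in both the primary tumor lesion and lymph node specimens assessed post-surgery". Section 9.2.4 defines MPR through "residual viable tumor cells histologically detected in the resected primary tumor and all resected lymph nodes after surgery".

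Baseline staging is described in several places. Section 3.1 gives clinical stage "as assessed by positron emission tomography/computed tomography (PET/CT" or, alternatively, by a work-up of CT, abdominal ultrasound, cranial MRI/CT and bone scintigraphy. Footnote 14 of Table 1 allows the same alternatives. Sections 4.1 and 6.2 name PET/CT only. Section 7.2.1 asks for one method and technique per lesion from baseline through treatment and follow-up.

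Table 1 schedules tumour imaging at screening, in Cycle 1 and at the end of neoadjuvant treatment. Section 6.4.4 specifies a CT at the end of Cycle 1. Treatment lasts 6-8 weeks.

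**The concern.** The endpoint asks whether cancer in the regional nodes has regressed by at least one N category. CT answers this indirectly, through node size, while histology of the resected nodes answers it directly. The definition uses the indirect measure in patients for whom the direct one is already in hand.

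Two problems follow. First, size and tumour content can disagree after treatment, so some patients will be placed on the wrong side of the endpoint. Second, a patient whose baseline N stage rests on PET/CT is compared with a scan that has no metabolic component, so part of any apparent change may come from the change of instrument.

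What is at stake is the credibility of one descriptive secondary endpoint in a trial of 25 patients, where one or two misclassified patients visibly move the reported percentage.

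**Working it through.** **No stated figure to reproduce.** The protocol gives no expected rate, power or sample size for nodal downstaging. The check is a comparison of definitions, followed by the arithmetic of misclassification.

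**Definitions side by side**

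| Endpoint | Evidence used for the nodes | Section |
|---|---|---|
| pCR | histology of resected nodes | 9.2.2 |
| MPR | histology of all resected nodes | 9.2.4 |
| Nodal downstaging | CT | 9.2.4 |

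Consider an operated patient with nodal disease at baseline.

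- The node shrinks to normal size but holds viable tumour. CT can record downstaging, while the specimen shows persistent disease and the patient fails pCR.
- The node is cleared but stays enlarged. CT can record no downstaging, while the specimen shows that nodal disease is gone.

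Both errors are open under the definition as written, and the pathology report would resolve either.

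**Weight of one patient.** The planned total is 25 (section 9.1).

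- If all 25 complete treatment, the protocol's own denominator gives 1/25 = 4 percentage points per misclassified patient.
- If the denominator were 15 node-positive patients, the figure is 1/15 = 6.7 points. The 15 is assumed; the document gives no node-positive count.

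**Net effect on the rate (illustration, all inputs assumed).** Among node-positive patients, let q be the true share downstaged on pathology, f the share of those not downstaged who look downstaged on CT, and g the share of those downstaged whom CT misses.

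CT rate = q(1 − g) + (1 − q)f

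CT rate − q = (1 − q)f − qg

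With g = 0, q from 0.30 to 0.70 and f from 0.10 to 0.40:

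- smallest excess: (1 − 0.70) × 0.10 = 0.03, or 3 points;
- largest excess: (1 − 0.30) × 0.40 = 0.28, or 28 points;
- middle case q = 0.50, f = 0.20: 0.50 × 0.20 = 0.10, so CT gives 60% against 50%. With 15 node-positive patients that is 15 × 0.10 = 1.5 patients, or 1.5/25 = 6 points on the completer denominator.

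With q = 0.50 and f = 0.20, but g above zero:

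- g = 0.20: 0.10 − 0.50 × 0.20 = 0, so the errors cancel in the rate although individual patients are still misclassified;
- g = 0.40: 0.10 − 0.50 × 0.40 = −0.10, so CT understates by 10 points.

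The sign depends on whether (1 − q)f exceeds qg. The document gives none of the three quantities, so the direction is open.

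**Change of method.** A patient staged by PET/CT at baseline and by CT afterwards is not assessed with one technique, which section 7.2.1 asks for. A patient staged through the CT-based work-up in section 3.1 does not have this problem. How many fall in each group is not stated.

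**The case against.** The strongest defence is that presurgical radiological downstaging is a coherent endpoint in its own right. It can be assessed in patients who complete treatment but are not operated, nodal pathology already enters pCR and MPR, and the endpoint is only summarised descriptively, with no test or decision rule. This stands as a reason to keep a CT figure and to treat the matter as an inexpensive improvement. It does not explain why the only nodal downstaging figure should ignore the specimens.

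A second objection is that the pathological definition also compares two methods: clinical stage at baseline and histology at surgery. A node falsely positive on baseline imaging would score as downstaged with no drug effect. That is true and remains a limitation of the remedy. The remedy removes the error at the post-treatment end only.

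Several stronger readings are tempting, but the documents do not support them.

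- *CT inflates the rate.* Not shown. Cleared nodes that stay enlarged err the other way.
- *An unchanged small PET-positive node will count as downstaged, because Appendix 3 says* "Nodes with short axis <10 mm are considered normal and should not be recorded or followed". That rule belongs to the RECIST appendix, which section 7.2.1 invokes for objective response. Staging follows AJCC 8th edition, and 9.2.4 sets no CT size rule for N stage. A reader who kept to the same-technique rule would not score such a node as downstaged.
- *Downstaging with residual nodal cancer in one patient is a contradiction.* Not in itself. A genuine fall from N2 to N1 leaves nodal cancer and fails pCR, and would do so under a pathological definition too.
- *The 6-week scan does not exist for patients treated for 8 weeks.* This holds only if the phrase means at week 6. It can equally mean after at least 6 weeks of treatment, which fits the end-of-neoadjuvant scan. The wording is ambiguous, but no conflict with Table 1 is established.

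**Conclusion.** The point holds as a weakness of measurement. Section 9.2.4 rests nodal downstaging on CT alone while the resected nodes are collected and read for two other endpoints, so avoidable misclassification is possible in both directions. For PET/CT-staged patients the comparison also changes method, against section 7.2.1.

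Each misclassified patient is worth 4 points if all 25 complete treatment, and 6.7 points under an assumed denominator of 15 node-positive patients. The 3-to-28-point range is an illustration that assumes CT misses no cleared node; once that assumption is dropped, the bias can be zero or negative. A reader should therefore not conclude that the reported rate will be too high.

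The primary pCR endpoint and its two-stage test are not affected.

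**What to change.** In section 9.2.4, define the rate of lymph node downstaging as the proportion of patients whose pathological N stage in the resected nodes (ypN) is lower than their baseline clinical N stage, with patients without resected nodes counted as not downstaged.

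Keep CT-based N downstaging as a supplementary figure, taken at the end-of-neoadjuvant scan in Table 1, and remove the 6-week phrase.

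When the definition is rewritten, reconcile its completer denominator with section 9.2.5, which says "All analyses will be performed using the FAS". The rule for patients without resected nodes makes the endpoint computable in either set.

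The cost is one changed definition and no new procedure, since the pathology is already obtained for pCR and MPR. There are two downsides. The rate will probably be lower, partly because unoperated patients count as failures. Baseline stage also remains clinical, so a false-positive node at baseline would still score as downstaged; the report should say so.
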